Short Title	PATS (Pediatric Adenotonsillectomy for Snoring)
Special Population	Children (male and female), ages 3.0 to 12.9 years of age
Methodology	Parallel, randomized, single blind, multi-center design
Study Duration	5 years
Clinical Study Center(s)	Multicenter (7)
Objectives	
1. Determine the effect of early adenotonsillectomy (eAT) on behavior (primary outcome), sleep-disordered breathing (SDB) symptoms, and quality of life.
 
2. Determine the effect of AT on health care utilization (HCU) in children with MSDB.
 
3. Identify factors that moderate the response to surgery: age, socioeconomic status, asthma and atopy, second hand tobacco smoke exposure, family functioning, short sleep duration, obesity, minority status

Number of Participants	460
Diagnosis and Main Inclusion Criteria	Diagnosis of mild sleep-disordered breathing (MSDB) defined by an obstructive apnea index (OAI) <1/hr or an apnea hypopnea index (AHI) <or =3.0 /hr confirmed by nocturnal polysomnography (PSG); parental report of habitual snoring (on average occurring > 3 nights per week); tonsillar hypertrophy $\geq 2 +$; deemed to be a surgical candidate for adenotonsillectomy (AT) by ENT evaluation
Study Intervention	Early Adenotonsillectomy (eAT)
Reference Intervention	Watchful Waiting with Supportive Care (WWSC)
Duration of Follow-Up	12 months
Statistical Methodology	Primary analyses will follow the "intention-to-treat" principle; that is, individuals will be analyzed according to their assigned treatment group, whether or not they remain on the study treatment. The co-primary outcomes will be the change in executive behavior relating to self-regulation and organizational skills (as measured by the Behavior Rating Inventory of Executive Function [BRIEF2/P] Global Composite Score) and vigilance (as measured on the Go-No-Go [GNG]) between the eAT and WWSC groups at 12 months. Analyses addressing secondary aims will be considered exploratory. Details of the statistical plan are outlined in the Data Coordinating Center application.

Rationale for the PATS Study

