2.1. General Design

This will be a randomized, single-blind 12-month intervention study that compares the impact of AT on measures of behavior, quality of life and HCU in children with MSDB. The proposed study will involve participation of children and their caregivers. Children with symptoms of MSDB will be recruited from each site's sleep clinics and laboratories, otolaryngology clinics, asthma clinics and general pediatric clinics. Potentially eligible children who are reported to be snorers at each site will be identified through systematic screening of health records and parent interviews. Children who meet study eligibility criteria will be randomized to having either eAT or WWSC for 12 months. In addition to the enrollment PSG at baseline, participants will receive behavioral testing, assessment of SDB symptoms, sleepiness, quality of life, anthropometry, and blood pressure. PSG and baseline measures will be repeated at 12-months. At 6 months caregivers will complete neurobehavioral assessments remotely, except for Virginia , where they will have an in person visit with child neuro behavior testing. Potential factors that may affect response to AT will also be assessed (asthma and atopy, secondhand smoke exposure, , family functioning). Approximately 920 participants will undergo baseline screening PSG, and 460 participants will be randomized. Both genders and all racial and ethnic groups will be eligible for participation. Participants failing baseline screening PSG will be referred for clinical care. It is anticipated that ~50% of participants will be eligible after PSG.460 eligible children, 230 per treatment arm, will be randomized to one of two treatment groups, and followed for a 12-month period.

Eligible participants will be randomized to one of two management groups:

[figure not shown]
1. Early Adenotonsillectomy (eAT) performed by participating ENT surgeons within 1-4 weeks of randomization.
2. Watchful waiting with Supportive Care (WWSC)

Participants in both groups will receive verbal and written information about healthy sleep habits guidance. Participants will be referred for appropriate "usual care" for relevant co-morbidities (for example, poorly controlled asthma, allergies) identified by the study team as needing further optimization of management.

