4.2. Inclusion Criteria

1. Ages 3.0 to 12.9 years at the time of screening
2. Diagnosed with MSDB defined as:
 - a. Parent report of habitual snoring that occurs most of the night on at least 3 nights per week, and has been present for at least 3 months (on average occurring > 3 nights per week or more than one-half the sleep time) *and*
 - b. Obstructive apnea index < 1/hr or obstructive apnea hypopnea index < 3 /hr and no desaturation < 90% in conjunction with obstructive events, confirmed on nocturnal, laboratory-based PSG

NOTE: Participants failing baseline screening PSG will be referred for clinical care.

3. Tonsillar hypertrophy ≥ 2 based on a standardized scale of 0-5
 - a. 0 = surgically absent
 - b. 1 = taking up < 25% of the space between the tonsillar pillars
 - c. 2 = taking up 25-50% of the space between the tonsillar pillars
 - d. 3 = taking up 51-75% of the space between the tonsillar pillars
 - e. 4 = taking up > 75% of the space between the tonsillar pillars
4. Deemed to be a candidate for AT by ENT evaluation, i.e., no technical issues that would be a contraindication for surgery such as submucous cleft palate.
5. Primary indication for AT is nocturnal obstructive symptoms (i.e., not recurrent infections or other indications)

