Aim 1: We will use the Wilcoxon rank-sum test to compare group changes in secondary behavior/performance measures including the GNG inhibitory control d'-prime and the average of the sustained attention d-prime and inhibitory control d-prime, SDB symptoms and quality of life endpoints over the 12-month study period. Generalized linear regression models will be used to model treatment effects adjusting for covariates. All outcomes other than PSG indices will be available at 6 months and 12 months and thereby can be analyzed using the mixed effects model outlined for the primary analysis, which does not assume a linear trajectory over time. For continuous outcomes which appear to have a linear trajectory over time, we will also estimate the rate of change in each treatment group and test the null hypothesis that the rates of change are equal for the eAT group and the WWS group using the following mixed effects model:

Let T denote time and $T=0, 1, 2$ refer to baseline, month 6 and month 12. Let X_3 denote the treatment indicator as before. The model will have each of the outcomes as response and include the main effects of T and the interaction effect of $T \times X_3$. The coefficient for $T \times X_3$ represents the treatment effect on linear trajectories.

Standard methods can be used to estimate this effect and test the null hypothesis of a zero effect.

For PSG indices (e.g., metrics of overnight hypoxemia, hypercapnia, sleep architecture, and breathing patterns) that are only available at baseline and 12 months, similar models can be used except that the variables corresponding to 6 months will be removed from the model. All participants enrolling in PATS entered the trial with an apnea-hypopnea index (AHI) under 3, i.e., without any evidence of obstructive sleep apnea syndrome (OSA). Estimating the proportion of participants who went on to develop OSA during the trial is thus of particular interest. We will also evaluate treatment effects on the proportion of participants with emergence of OSA (as defined by an $AHI \geq 3$) and 5 (indicating emergence of moderate or more severe OSA) at 12 months, and whether treatment effects differ by subgroups specified in Aim 3.

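### The 12-month AHI ≥3 outcome reuses the single-night entry cut-off, so its crude proportion overstates how many children developed OSA

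*Combined protocol and SAP*

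**What the plan says.** Under Secondary Analyses, Aim 1, the SAP states: "All participants enrolling in PATS entered the trial with an apnea-hypopnea index (AHI) under 3". It takes this to mean that no child had OSA at entry and adds: "Estimating the proportion of participants who went on to develop OSA during the trial is thus of particular interest". Emergence is a 12-month AHI of 3/hr or more. A second cut-off of 5 is described as "indicating emergence of moderate or more severe OSA) at 12 months". Treatment effects on both proportions are planned as well.

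Section 9.1 provides one PSG at entry and one at 12 months. The SAP confirms that PSG indices exist only at those two times. I found no repeat night, minimum rise from baseline, confirmatory criterion or allowance for selection on the baseline value.

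The entry rule is worded in three ways:
- Section 4.2, item 2b: "Obstructive apnea index < 1/hr or obstructive apnea hypopnea index < 3 /hr and no desaturation < 90% in conjunction with obstructive events".
- Study Summary: "apnea hypopnea index (AHI) <or =3.0 /hr confirmed by nocturnal polysomnography (PSG".
- SAP: AHI under 3, as quoted above.

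On screening yield, section 2.1 says: "It is anticipated that ~50% of participants will be eligible after PSG".

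**The concern.** Children are selected because one noisy measurement fell below 3, and are then counted if the next noisy measurement reaches 3. Some of those selected had a low night by chance, and on a second night they drift back up. A child at 2.9 and then 3.0 is a new case under this definition. Counts of this kind arise even if no child's condition changes.

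The SAP announces estimation of the proportion itself, separately from the treatment effect. Randomisation protects the difference between arms. It does not protect a proportion within one arm. The WWSC figure is the one at risk, because it would be taken as the rate at which untreated mild sleep-disordered breathing progresses and so bears on how safe waiting appears.

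**Working it through.** **1. The plan's own figures.** Screening yield: 920 × 0.50 = 460 randomised, as stated. Evaluable at 12 months: 460 × 0.80 = 368, as stated, or 184 per arm. The documents give no expected OSA incidence, no power for this outcome and no reliability for AHI.

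**2. Model with no true change.** Log AHI on the two nights is taken as bivariate normal with the same distribution and correlation r. Let q be the share of screened children who pass the AHI test itself, and c the standardised cut-off, so that Φ(c) = q. Then

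P(second ≥ 3 | first < 3) = 1 − Φ₂(c, c; r) / q,

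which at q = 0.5 becomes 1/2 − arcsin(r)/π. Here r is short-term reliability. It is an assumption, and so is the normal shape.

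- r = 0.6: 0.5 − 0.6435/3.1416 = 0.295; × 184 = 54
- r = 0.8: 0.5 − 0.9273/3.1416 = 0.205; × 184 = 38
- r = 0.95: 0.5 − 1.2532/3.1416 = 0.101; × 184 = 19

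**3. Range over r and pass share.** Crossings with no true change, with the count out of 184 in brackets:

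| AHI pass share | r = 0.6 | 0.7 | 0.8 | 0.9 | 0.95 |
|---|---|---|---|---|---|
| 50% | 29.5% (54) | 25.3% (47) | 20.5% (38) | 14.4% (26) | 10.1% (19) |
| 70% | 18.2% (33) | 15.6% (29) | 12.7% (23) | 8.9% (16) | 6.3% (12) |
| 90% | 6.8% (12) | 5.9% (11) | 4.9% (9) | 3.5% (6) | 2.5% (5) |

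**4. Counting variation only.** As a lower bound near the 50% pass share, each child was given an identical true rate on both nights and only Poisson variation in event counts was simulated (7–9 hours of sleep, SD of log AHI 0.6–1.5, all assumed). Crossings were 6–16%. In the same simulation 4–10% of children who passed screening already had a true rate of 3 or more, so they were misclassified at entry.

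**5. The cut-off of 5.** At a 50% pass share and SD of log AHI 0.6–1.5 (assumed), the model gives 6–18% at r = 0.6, 2–10% at r = 0.8 and 0–2% at r = 0.95. This cut-off is less affected.

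**6. Effect on a reported figure.** Suppose 5% truly progress, r = 0.8 and the pass share is 50%. The crude proportion would be 0.205 + 0.795 × 0.05 = 0.245, nearly five times the truth.

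**7. The randomised comparison.** With equal crossing probabilities of 14–25% in both arms and 184 per arm, the simulated rejection rate of Fisher's test at the 5% level was 3–4%. There is no inflation of type I error.

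**The case against.** **The size is not established.** This stands. Reliability is not in the documents. A 12-month correlation cannot stand in for it, because it also falls when children truly progress or remit. The 50% yield need not place the AHI cut-off at the median either: section 4.2 also excludes desaturation below 90% with obstructive events, and the SAP says the PSG screens out other sleep disorders. Children failing only on those grounds push the AHI pass share above 50% and the crossings down, so a reader who took the top of the 50% row as the answer would overstate the problem.

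**The figures should not be applied to all 368 children.** Agreed. A reader might pool the arms, but the Rationale reports that surgery improved polysomnographic parameters in the earlier trial in OSA. No change is therefore not a credible null for the surgical arm.

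**The treatment comparison is not biased.** Agreed. A reader might still infer a large loss of power. For a true 10% versus 0% at r = 0.8 and a 50% pass share, power falls from about 99% to 43%, but only if chance crossings are equally common in both arms. If surgery lowers AHI they are not, so that loss is not shown.

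**The index may be the same throughout.** A reader might infer that central events counted in the 12-month AHI would create cases among unchanged children. The SAP's own statement that everyone entered with AHI under 3 contradicts the example this needs, since such a child would already exceed 3 in total AHI at entry. Loose terminology is the likelier explanation, and scoring detail sits in a PSG manual that is not available here. What stands is that the wordings differ.

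**Much of the remedy is already planned, and the outcome is exploratory.** Both are true. Between-arm effects, the second cut-off and baseline/12-month models for PSG indices are in the SAP. AHI of 3 or more is also the protocol's trigger for ENT re-referral, so the crude count has operational meaning. None of this supports reading it as the number who developed OSA.

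**Conclusion.** The point holds for the within-arm proportion. The direction of the error follows from the design alone: the same cut-off at entry and outcome, one night at each, and no safeguard. The size is a range, 3–30% over the pass shares and reliabilities considered, resting on the bivariate normal model. No single incidence correction can be drawn from the documents.

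The inconsistent entry wording adds a smaller point. Under the Study Summary a child at exactly 3.0 meets the outcome definition at baseline. Read literally, the alternative in section 4.2, "Obstructive apnea index < 1/hr or obstructive apnea hypopnea index < 3 /hr", admits a child with an obstructive apnea index below 1 and an AHI of 3 or more. Either reading conflicts with the SAP's premise about entry.

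No primary result, alpha allocation or sample size is affected. The change is still worth making, because the SAP singles this proportion out.

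**What to change.** In Secondary Analyses, Aim 1:

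1. Name the outcome *12-month AHI ≥3 (≥5) on a single PSG*. Delete the statement that the proportion estimates how many children developed OSA. Add a caveat that crude proportions include crossings due to selection on the baseline value.
2. Make the between-arm difference, adjusted for baseline AHI and the stratification factors, the inferential result. Analyse 12-month AHI on a continuous, transformed scale alongside it.
3. Score the outcome on the index used at entry, and reconcile the Study Summary, section 4.2 item 2b and the SAP on what that index and limit are.

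I would not add a model-based expected proportion beside each arm. It needs a reliability figure from outside the documents and would be driven by assumption, most of all in the surgical arm.

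The cost is a few lines of SAP text and no new data. The price is that the crude proportion can no longer be presented as incidence.

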- c) Any differences in outcomes (BRIEF2/P, GNG, HCU) between children randomized to eAT or to WWS will not vary by age, baseline overweight/obesity, atopy/asthma status, secondhand smoke exposure, family and neighborhood socioeconomic status, family functioning, baseline symptom severity (i.e., Sleep Disordered Breathing Scale) or race (African American vs other; Minority vs. non-minority).

Exploratory Analyses

Analyses addressing secondary hypotheses will be considered exploratory. These include mediation and moderation analyses.

As snoring is the focus of this study, we will assess the association between quantitative estimates of snoring with study outcomes at baseline, evaluate the treatment effect on these snoring measurements, and whether changes in snoring correlates with changes in study outcomes, as an exploratory analysis.

Variables Used to Stratify Randomization

Randomization will be stratified by the following factors within site: age (\leq 5 years vs $>$ 5 years); overweight status (body mass index [BMI] $>$ 85%ile); and race (African American vs other). These represent key groups likely to influence treatment responses.

Stratification by these factors will provide greater assurance that the comparison groups will be similar with respect to these and related variables. Given an overall sample size of 460 and a relatively large number of strata (8 strata within each of the 5 sites), we will use a dynamic randomization method, Pocock and Simon's minimization method⁷¹, implemented in the Data Management System (Slice), to ensure treatment arms are balanced with respect to these factors as well as for the number of subjects in each group. Because the minimization method is more complex than stratified permuted blocks, [name] will monitor the randomization assignment closely to ensure the integrity of randomization.

Estimated Power and Sample Size

The study plans to randomize 460 subjects into one of the two arms in a 1:1 ratio. Based on the experience in the CHAT study, we assume a dropout rate of 15% at 6 months, and an additional 5% attrition at 12 months, resulting in 390 and 368 evaluable subjects at 6 and 12 months, respectively. As described below, this sample size was chosen so that the study will have ample power to detect moderate to large moderation effects and a range of mediation effects when the exposure-moderator and moderator-outcome associations are moderate or large.

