The power to detect potential mediation effects (see below) depends on not only the mediation effect, but also on the magnitude of the association between exposure (X) and mediator (M) and the association between outcome (Y) and mediator controlling for exposure. As determined in simulation studies by Fritz and MacKinnon⁷⁶, a sample size of 368 achieves greater than 80% power to detect mediation effects ranging from small, to medium, to large (corresponding to a path coefficient of 0.14, 0.39 or 0.59) for the settings with moderate to large X-M and M-Y associations using various resampling methods including the PRODCLINC program⁷⁷, the percentile bootstrap, and bias-corrected bootstrap methods⁷⁸. For the settings where one of the X-M and M-Y associations is small, a sample size of 368 achieves close to 80% power if the other association is moderate or large using the bias-corrected bootstrap method.

Approaches to the Analysis

Primary analyses will follow the “intention-to-treat” principle; that is, individuals will be analyzed according to their assigned treatment group, whether or not they receive the study treatment as assigned. This approach avoids bias if individuals drop out of the two arms for different reasons. Every effort will be made to obtain follow-up data on all children randomized, whether or not they follow their assigned treatment. Although every effort will be made to minimize missing data, some missing data will be inevitable, and therefore a variety of methods that accommodate missing data in analyses will be

considered, including inverse probability weighting and multiple imputation. For example, missing covariates may be imputed through the multiple imputation through chained equations (MICE) approach⁷⁹ and missing outcomes may be handled through the use of mixed effects modeling or inverse probability weighting^{80 81}. We will make explicit the assumptions for the methods employed and perform sensitivity analyses to assess the robustness of results to plausible violations of these assumptions. Sensitivity analyses will be conducted excluding children on ADHD medications.

Preliminary Analyses

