If we observe differences in behavior and vigilance between groups, we will determine whether improvements in vigilance explain a significant portion of the improvement in behavior, using the steps to establish mediation outlined by Baron and Kenny⁸⁴, which consist of fitting a series of regression models and testing relations among variable corresponding to significance tests of the regression coefficients. Specifically, we will construct regression models with change from baseline to 12 month BRIEF2/P GEC score as the outcome, including a treatment indicator as an independent variable, with and without including the change in the Go-No-Go performance test as a covariate. We will compare the coefficients for the treatment indicator to examine how much of treatment effect on the BRIEF2/P is explained by changes in the GNG test. Point and interval estimates for the reduction in the coefficients will be provided. Similarly, if sleep duration (by actigraphy and parent report) and sleep-quality (by PSG and parent report) demonstrate treatment effects, we will explore these factors as potential mediators for changes in behavior and vigilance (if these outcomes show treatment effects).

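### The mediation power quoted in the SAP is for bootstrap and product-of-coefficients tests; the planned Baron-Kenny steps have much less power when the total effect is small

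*Combined protocol and SAP*

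**What the plan says.** All of this is in Section 19, Statistical Analysis Plan.

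- **Sample-size rationale (Estimated Power and Sample Size).** 460 children are randomized 1:1, "resulting in 390 and 368 evaluable subjects at 6 and 12 months, respectively". The size is said to have been chosen partly to give "ample power to detect moderate to large moderation effects and a range of mediation effects".
- **Mediation power (last paragraph under the same heading).** The plan states that "a sample size of 368 achieves greater than 80% power to detect mediation effects ranging from small, to medium, to large" when both associations are moderate to large; it sets small, medium and large paths at 0.14, 0.39 and 0.59. The methods behind this figure are described as "various resampling methods including the PRODCLINC program", together with two forms of bootstrap (percentile and bias-corrected). When one association is small and the other moderate or large, the figure is close to 80%, and that figure is tied to the bias-corrected bootstrap alone.
- **Mediation analysis (Secondary Analyses, Aim 1).** If the arms differ on behavior and on vigilance, mediation of the BRIEF2/P GEC effect through the Go-No-Go (GNG) score is assessed "using the steps to establish mediation outlined by Baron and Kenny", that is, by a series of regressions judged by significance tests of their coefficients. The treatment coefficient is compared with and without the mediator, and a point and interval estimate of its reduction is promised. No interval method is named. Sleep duration and sleep quality are handled similarly, again only if treatment effects are seen.
- **Status (Exploratory Analyses).** Mediation analyses are classed as exploratory.

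No part of the plan names a bootstrap or product-distribution method for the analysis, and none gives power for the causal steps.

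**The concern.** The two families of test have different requirements. A bootstrap or product-distribution test asks whether the indirect effect, a times b, differs from zero; here a is the effect of treatment on the mediator and b is the effect of the mediator on the outcome given treatment. The causal steps also require a detectable total effect c of treatment on the outcome. When mediation is complete, c equals a times b. A product of two moderate paths is small, so the total-effect step can fail while both paths are clearly present.

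At stake is the meaning of a null mediation finding. A reader relying on the power paragraph would take such a finding, or the absence of a mediation analysis, as fairly strong evidence that vigilance does not carry the effect on behavior. Under the planned steps it might only mean that the total effect was too small to pass. A stated reason for the sample size also rests on power for a test that is not the one planned.

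**Working it through.** **Inputs from Section 19.** N = 368 (184 per arm). Path sizes 0.14, 0.39 and 0.59. GEC: difference 3.7, SD 11.5, baseline to follow-up correlation 0.73. GNG: difference 0.33, SD 0.77, correlation 0.48.

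**Assumptions.** The plan gives no significance level for mediation, so two-sided 0.05 is used. The model is M = aX + e and Y = c'X + bM + e, with unit residual SDs. The causal steps count as passed when c, a and b are each significant. Reading the entry condition as a significance test is an inference, because the plan sets no level for it.

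**Step 1: the plan's figures with the plan's methods.** Treatment is scaled to unit variance, with no direct effect (c' = 0), 1,000 simulated trials per row and 1,000 resamples (500 trials for the product distribution). The Monte Carlo standard error is at most about 1.6 points (2.2 for the product column).

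| a | b | Percentile bootstrap | Bias-corrected bootstrap | Product distribution | Causal steps |
|---|---|---|---|---|---|
| 0.14 | 0.39 | 77% | 79% | 77% | 16% |
| 0.39 | 0.14 | 75% | 77% | 77% | 14% |
| 0.14 | 0.59 | 78% | 78% | 76% | 27% |
| 0.59 | 0.14 | 79% | 80% | 81% | 27% |
| 0.39 | 0.39 | 100% | 100% | 100% | 76% |
| 0.39 | 0.59 | 100% | 100% | 100% | 97% |
| 0.59 | 0.39 | 100% | 100% | 100% | 98% |
| 0.59 | 0.59 | 100% | 100% | 100% | 100% |

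The stated power is reproduced: above 80% when both paths are moderate or large, and close to 80% with one small path. The last column is the planned procedure. A separate run of the 0.14/0.39 row gave 14%.

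**Step 2: why it drops.** Take the first row, with √368 = 19.18 and critical value 1.966.

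- Path a: z = 0.14 × 19.18 = 2.69, power 76%.
- Path b: z = 0.39 × 19.18 = 7.48, power about 100%.
- Total effect: c = 0.14 × 0.39 = 0.0546; z = 0.0546 × 19.18 / √(1 + 0.39²) = 0.98, power 16%.

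The total-effect step is the bottleneck.

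**Step 3: the plan's own vigilance effect.**

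- GNG change SD = 0.77 × √(2 × 0.52) = 0.785, so a = 0.33 / 0.785 = 0.42 SD between arms.
- GEC change SD = 11.5 × √(2 × 0.27) = 8.45, so the assumed total effect is 3.7 / 8.45 = 0.44 SD.
- With b = 0.39, the a step has z = 0.42 × 19.18 / 2 = 4.03 and power 98%. Joint significance of a and b, which tracks the percentile bootstrap closely, is therefore 98% throughout.
- With no direct effect, c = 0.42 × 0.39 = 0.164. Dividing by √(1 + 0.39²) = 1.073 gives 0.153 SD; z = 0.153 × 19.18 / 2 = 1.46, power 31%.

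| Total effect on GEC | Causal steps (simulated) | Joint test of a and b |
|---|---|---|
| 0.15 SD (no direct effect) | 29-32% | 98% |
| 0.2 SD | 41-48% | 98% |
| 0.3 SD | 75-82% | 98% |
| 0.44 SD (plan) | 96-97% | 98% |

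The ranges cover repeat runs and whether the total effect is scaled by the SD of Y given arm or by the residual SD.

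**Step 4: when the loss disappears.**

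- With a direct effect of 0.14 or 0.39 (unit-variance scale) and paths 0.14 and 0.39 in either order, the causal steps give 74-77% against 79-81% for the bias-corrected bootstrap.
- At the plan's assumed effects (a = 0.42 / 2 = 0.21 and c = 0.44 / 2 = 0.22 on that scale), the causal steps give 72%, 97% and 97% for b = 0.14, 0.39 and 0.59. The bias-corrected bootstrap gives 80%, 99% and 98%. Most of the 8-point gap at b = 0.14 is not due to the total-effect step: joint significance alone gives 73% there.

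**Scale.** Step 1 reproduces the plan only with treatment at unit variance. With 0/1 coding, a = 0.14 and b = 0.39 gives 28% even with the bias-corrected bootstrap. The plan does not say which scale it means.

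**The case against.** The strongest reply has four parts.

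**The large losses occur at effects the plan does not assume.** This stands. The 0.15 and 0.2 SD cases are about 1.3 and 1.7 GEC points (0.153 × 8.45 and 0.2 × 8.45). The plan's own minimum detectable difference is 2.4 points at 80% power and the 5% level. At 2.4 points the causal steps would have roughly 0.80 × 0.98 = 78%. Against this, the 3.7-point assumption comes from children with frank OSA in the earlier trial, and whether milder disease responds is what this trial asks.

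**The gate partly follows from the question.** The plan asks how much of an improvement in behavior is explained by vigilance; without an improvement there is nothing to apportion. This also stands in part. Testing the indirect effect regardless of the total effect is a somewhat different question and adds exploratory tests.

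**The plan already promises an interval for the coefficient reduction.** In linear models fitted to the same children, that reduction equals a times b, so the right quantity is already in the plan. But the interval method is unnamed, the interval is not made the basis of the decision, and the entry condition still applies. The Aim 3 models for race differences mention a product term too, but only as an alternative and only if race differences are found.

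**The analysis is exploratory, and the sample size would not change.** The plan reports 98% power for each co-primary outcome, so this is right as far as it goes. It does not make the quoted mediation power correct for the planned test.

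**Conclusion.** The mismatch is real: the mediation power in Section 19 describes tests that the plan does not name for the analysis. Its size depends on the total effect. With no direct effect and one small path, power falls from about 75-80% to about 13-27%. With the plan's vigilance effect and b = 0.39, it is about 30% against 98% with no direct effect, and about 45% against 98% at a total effect of 0.2 SD. At the assumed 0.44 SD the loss is about 1 to 8 points. These figures assume a single-mediator linear model, a two-sided 0.05 level at each step, and the entry condition read as a significance test.

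A reader might infer more than the documents support:

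- *That the trial is generally underpowered for mediation, or that mediation will usually be missed.* The loss nearly disappears at the effects the plan assumes.
- *That the sample size or the primary conclusions are in doubt.* Mediation is exploratory, and the co-primary powers recompute to within 2 points of the stated 98%.
- *That the same losses are shown for the sleep mediators.* The plan gives no treatment effect on sleep duration or quality, so none can be computed. Only the mismatch of method carries over.

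**What to change.** In Secondary Analyses, Aim 1, make a percentile or bias-corrected bootstrap interval for a times b the mediation test, for the vigilance mediator and the sleep mediators. State that it is the interval already promised for the coefficient reduction, that a significant total effect is not required, and that the analysis is exploratory. The power paragraph then describes the test used. In that paragraph, also state the significance level and the scale of the path coefficients.

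The cost is SAP wording and a few lines of code, with no new data or visits. The small downside is a few more exploratory tests, reported as such.

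If the causal steps and the entry condition are kept because the question is about apportioning an observed effect, define the entry condition. Say also that the quoted power does not apply to the steps, and give their power as a function of the total effect, as in the second table above.
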